Effects of Tai chi Chuan on cognitive function in Adults 60 years
old or older with type 2 diabetes and mild cognitive impairment:
A Randomized Clinical trial

4

5

Study Protocol

6 Introduction

7 Type 2 diabetes mellitus (T2DM) is a chronic metabolic disorder characterized by sustained hyperglycemia and insulin resistance¹. 8 According to the International Diabetes Federation, the number of 9 patients in China of having diabetes mellitus was about 1.409 million, 10 which represented a sharp increase compared to the results of the same 11 survey conducted in 2019 $(1.289 \text{ million})^2$, nearly 95% of diabetic cases 12 are T2DM³. Cognitive impairment is a common comorbidity of diabetes, 13 especially in elderly populations⁴. Mild cognitive impairment (MCI) is a 14 prodromal stage of Alzheimer's disease⁵. Our previous Meta analysis 15 found that about 45% of people with diabetes have MCI⁶. The rate of 16 conversion from MCI to dementia is 1.5-3 times higher in diabetic 17 patients than in non-diabetic patients⁷. Impaired cognitive function may 18 cause impaired self-management in people with diabetes, worsening their 19 condition. 20

21

22 It is critically important to identify effective treatments to enhance cognitive function of T2DM patients with MCI. Exercise is typically one 23 of the first management strategies advised for patients with T2DM⁸. Tai 24 Chi Chuan, a Chinese traditional mind-body exercise, incorporates 25 physical, cognitive, social, and meditative components in the same 26 activity⁹. Research shows that Tai chi Chuan is to be helpful in global 27 cognitive function, memory and learning, visuospatial ability, and 28 executive functions of MCI¹⁰, and metabolic control of T2DM¹¹. 29 However, the evidence of the effect of Tai Chi Chuan on T2DM patients 30 with MCI is limited. Therefore, we designed a multi-centre, randomised, 31 parallel controlled clinical trial to explore the effect of Tai Chi Chuan 32 treating T2DM patients with MCI in cognitive function. 33 34

35 Methods

36 **Participants**

37 **Diagnostic criteria**

The diagnosis of T2DM is based on the 2018 American Diabetes Association and World Health Organization criteria^{12, 13}. MCI is diagnosed using the criteria of Petersen¹⁴.

42 Inclusion criteria

We will include eligible participants: (1) clinician diagnosis of T2DM; (2)
presence of mild cognitive impairment, not demented; (3) age ≥ 60 years
old; (4) did not engage in regular exercise in the last three months (at
least 3 times a week, at least 20 minutes of regular exercise each time);
(5) informed consent and voluntary participation.

48

49 T2DM diagnosis criteria:

According to the American Diabetes Association diagnosis criteria for 50 T2DM: FPG \geq 126 mg/dL (7.0 mmol/L). Fasting is defined as no caloric 51 intake for at least 8 h; or 2-h PG \geq 200 mg/dL (11.1 mmol/L) during 52 OGTT. The test should be performed as described by WHO, using a 53 glucose load containing the equivalent of 75 g anhydrous glucose 54 dissolved in water; OR A1C \geq 6.5% (48 mmol/mol). The test should be 55 performed in a laboratory using a method that is NGSP certified and 56 57 standardized to the DCCT assay; OR In a patient with classic symptoms of hyperglycemia or hyperglycemic crisis, a random plasma glucose ≥ 200 58 mg/dL (11.1 mmol/L). 59

(DCCT, Diabetes Control and Complications Trial; FPG, fasting plasma
glucose; OGTT, oral glucose tolerance test; WHO, World Health
Organization; 2-h PG, 2-h plasma glucose.)

63

64 MCI diagnosis criteria:

According to the Peterson criteria for MCI: Cognitive impairment is
confirmed by patients or informed persons or experienced clinicians;
There is one or more cognitive aspects impairment (memory, language,
visuospatial or executive function); Functional activities are basically
normal; No dementia.

70

71 Exclusion criteria

Patients will be excluded who: (1) cognitive impairment caused by other
reasons, taking drugs, poisoning, etc; (2) presence of medical conditions
that unable or unsafe to exercise, such as depression symptoms,

vuncontrolled hypertension/ blood pressure/ blood glucose, nervous system

76 diseases(stroke, Parkinson's disease, etc), musculoskeletal system

diseases(arthritis, history of hip and/or knee joint replacement, etc), etc;

78 (3) participating in other experiments that influence this study.

79

80 Sample size

Based on a previous study and a pilot study we did¹⁵, A sample size of approximately 109 participants per group calculated using PASS (considering 20% dropout rate) was determined to provide 80% power to achieve statistical significance at the 5% 2-sided level for comparisons of the two intervention groups (Tai Chi Chuan and fitness walking) versus control across primary end point. Comparisons between Tai Chi Chuan and fitness walking were not made due to lack of trial data.

89 **Randomization and concealment**

This study was a multicenter, randomized controlled clinical trial. 90 Subjects were randomized 1:1:1 into Tai Chi Chuan group, fitness 91 walking group, and control group using a central web-based 92 randomization system for group randomization (group size of 6). Because 93 blinding is not possible for participants in exercise-intervention 94 researches, the study outcome assessors and statistical analysts will have 95 no knowledge of the participants' study group. Blinding was discovered 96 after the statistical analysis of the study was completed. 97

98

99 Ethics

100

The study adheres to the Helsinki Declaration. The clinical trial has been approved by the Regional Committee on Medical Research Ethics from four partner institution: (1) The Second People's Hospital Affiliated to Fujian University of Traditional Chinese Medicine, Fuzhou, Fujian, China (approval No. 2020KY-004-02), (2) The Second People's Hospital 106 Affiliated to Heilongjiang University of Traditional Chinese Medicine (approval No.2020-K24), (3) Xiyuan Hospital of China Academy of 107 Chinese Medical Sciences, Beijing, China (approval No. 2020XLA033-108 2), and (4) Shenzhen Bao'an District People's Hospital, Shenzhen, China 109 (approval No.BYL20200409). All participants provided written informed 110 111 consent. Furthermore, a Data Security and Monitoring Committee has been established. The study was registered with https://clinicaltrials.gov/. 112 (Register Number: NCT04416841). 113

114

115 **Recruitment**

Volunteers will be recruited from the communities of Fuzhou of Fujian 116 117 Province, Harbin of Heilongjiang Province, Beijing Municipality, and Shenzhen of Guangdong Province. We will contact each patient, invite 118 them to participate, and schedule an individual appointment after a 119 combination of advertisements and enrollment through clinics. Patients 120 who are interested in participating will be given an explanation of the 121 study and will be able to choose whether or not to participate voluntarily. 122 If they agree to participate in the study, a clinical research coordinator 123 (CRC) will evaluate their suitability using inclusion and exclusion 124 criteria. Eligible subjects will sign an informed consent form before being 125 randomly assigned to one of three groups: Tai Chi Chuan, fitness 126 walking, or control. The flowchart is shown in Figure 1. 127

[figure not shown]

Figure 1. Flow chart for patient inclusion and follow up

132

131

133 Interventions

Clinical endocrinologist will give a lecture on the subject to all subjects, 134 including diabetes knowledge, proper diet, blood glucose monitoring, and 135 complications prevention, etc., for 0.5 hours per time, once per 4weeks 136 for 24 weeks. In addition, participants assigned to the Tai Chi Chuan and 137 fitness walking groups will engage in one hour of exercise three times a 138 week for 24 weeks under the supervision of physical education instructors 139 with more than five years of teaching experience. All sessions will 140 include: 141

128

142 a. Warm-up (10 min)

143 b. Aerobic component (40 min):

144 **Tai Chi Chuan group:** would take 24-form simplified Tai Chi Chuan.

Fitness walking group: would take fitness walking training, the exercise intensity was 50% to 70% of the maximum heart rate.

147 c. Cool-down (10 min)

148

Participants who were assigned to control group did not received exercise intervention and maintained their previous lifestyle. The participants were also encouraged to continue exercise after completing their 24 weeks interventions, throughout 36 weeks of follow up.

153

154 Outcomes

Outcomes will be evaluated at baseline, 24 weeks, and 36 weeks. The 155 primary end point was Montreal cognitive assessment scale (MOCA) at 156 36 weeks. Secondary outcomes include the primary outcome at 24 weeks, 157 as well as other cognitive subdomain tests and blood metabolic indices at 158 24 and 36 weeks. Cognitive subdomain tests include: (1) Wechsler 159 160 memory scale (WMS); (2) Digit Symbol Substitution Test (DSST); (3) Trial making test part B (TMT-B); (4) Boston naming test (BNT); (5) 161 Rey-osterrieth complex graphics test (ROCF). Blood metabolic indices 162

included fasting glucose, glycated hemoglobin (HbA1c), homeostasis
model assessment of insulin resistance (HOMA-IR), advanced glycation
end products/soluble receptor of advanced glycation end products
(AGE/sRAGE).

167 Measure

168 **Demographics**

At the first assessment, data on demographic characteristics will be collected: gender, age, years of education, duration of diabetes, diabetes medication, and history of disease, etc. were gathered by self-report. Height and weight were measured on site. Subjects were asked to wear light clothing and no shoes to record weight to the nearest 0.1 kg. Height was recorded to the nearest 0.5 cm. Body Mass Index (BMI) was calculated as weight (kilograms) divided by the square of height (meters).

177 cognitive performance measures

*MOCA*¹⁶: This scale is an assessment tool for global cognition. Scores range from 0 to 30, with higher scores indicating better cognitive functioning and scores below 26 indicating MCI.

181

182 WMS^{17} : We used the WMS for evaluation of memory function.

Wechsler's Memory Quotient (MQ) has a score range of 51 to 150, withhigher scores are considered to represent better memory.

185

DSST¹⁸: The Test test assesses attention and consists of a pairing of numbers and symbols. Symbols occur in the upper boxes and numbers in the lower boxes of a paired key. Participants then choose a target symbol that corresponds to a number, The number of correct numbers chosen within 90 seconds constitutes the score.

191

 $TMT-B^{19}$: We used the TMT-B for evaluation of executive function, The TMTB includes the numbers 1-25 in circles and squares and requires the participant to arrange the numbers from smallest to largest as quickly as possible while ensuring that the two shapes are connected alternately, and the evaluator records both the number of connection errors and the time, with shorter completion times and fewer connection errors indicating better performance.

199

 BNT^{20} : The BNT was used to assess language fluency. Subjects were asked to name the 30 objects/items printed on the card and the assessor recorded the number of correct names.

203

204 $ROCF^{21}$: Copy and delayed recall will be administered as a measure of

graphic memory function. Patients were asked to copy the ROCF as
accurately as possible on a piece of paper. after an interval of 20 minutes,
patients were asked to recall and draw the graph optimally.

208

209 Blood metabolism index

Subjects were asked to fast overnight and venous blood was drawn on an 210 empty stomach the next morning. Blood levels of fasting glucose, 211 HbA1c, insulin, AGE, and sRAGE were analyzed. HOMA-IR index 212 calculated from intravenous glucose and insulin levels: HOMA-IR = 213 [fasting insulin (μ IU/ml) × fasting glucose (mmol/L)]/22.5²². Aliquots of 214 serum will be stored at -80'C and used for AGE and sRAGE assays. 215 Serum concentrations of AGE and sRAGE were measured by ELISA kits 216 according to the manufacturer's instructions (AGE:HUFI00449, Human 217 AGE ELISA Kit, ReagentGenie, Ireland; RAGE: EK0827, Human RAGE 218 ELISA Kit, Boster, China). All assays will be performed according to the 219 manufacturer's instructions. AGE levels (μ g/ml) were divided by sRAGE 220 levels (pg/ml) to gain the ratio $(\mu g/pg)^{23}$. 221

222

Data management

All participant data will be identified by a study ID for enrolled participants All data from the completed CRFs will be imported into the excel spreadsheet twice by two independent data entry officers in the proper format. This will be checked by another person to ensure its accuracy. Any errors made during data entry will be corrected by comparison with the original data. After completing the examination of the data, the data is imported into specific analysis software for analysis.

232 Statistical Analysis

Statistical analysis will be used for all data. All collected data (e.g.
MOCA, WMS, DSST, TMT-B, BNT, ROCF, etc.) will be compared for
all three groups. See the statistical analysis plan for details. Results with P
< 0.05 will be considered statistically significant.

237

238 Safety

Throughout the course of the trial, each participant's safety will be watched over. All adverse events will be recorded, such as the number of times hypoglycemia occurs, falls, etc. and the relevance to treatment was evaluated by professional researchers.

244 **Quality Control**

245 Researchers receive uniform and strict training and examination. The trail

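### No common adverse-event enquiry across arms, although exercise participants have 72 more scheduled contacts than controls, so recorded harms can differ through unequal surveillance

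*Combined protocol and SAP*

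**What the plan says.** Protocol, Safety, makes two general commitments: "Throughout the course of the trial, each participant's safety will be watched over", and "All adverse events will be recorded, such as the number of times hypoglycemia occurs, falls, etc". Professional researchers then judge whether each event is related to treatment. The section names no visit, interval, form, question, diary or recorder.

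SAP 4.1.2 (Data set) says how events are tabulated: number, category, severity and relationship to the intervention. Incidence of adverse reactions is calculated in the safety set. That set needs at least one intervention after randomization and documented safety indicators. The SAP adds nothing on how events are elicited.

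Protocol, Interventions, fixes the contact pattern. All arms receive the endocrinologist's lecture, covering "complications prevention, etc., for 0.5 hours per time, once per 4weeks" up to week 24. The Tai Chi Chuan and "fitness walking groups will engage in one hour of exercise three times a" week for 24 weeks, supervised by instructors. For the third arm: "Participants who were assigned to control group did not received exercise intervention and maintained their previous lifestyle".

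Protocol, Outcomes, gives the remaining contacts common to all arms: "Outcomes will be evaluated at baseline, 24 weeks, and 36 weeks". Neither the lectures nor the assessments are designated for collecting adverse events.

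**The concern.** The two events named as examples, falls and hypoglycaemia, can be brief and leave no trace unless someone asks about them soon afterwards. Participants are 60 or older with mild cognitive impairment, and memory is one of the domains that may be impaired, so recall over several weeks is a weak safeguard. Two arms meet study staff three times a week; the third does so about once every four weeks. With no enquiry common to all arms, opportunities to notice or mention an event are unequal by design.

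What is at stake is the harms comparison between exercise and control. If capture is better in the exercise arms, their event rates look relatively too high, and a real reduction in falls could appear as no effect or as harm. The multiple imputation and analysis-set rules do not help, because an event nobody elicited is not a missing value that the data set can recognise. The safety set may add to the problem: membership depends on documented safety indicators, and the SAP does not say whether a lecture counts as an intervention for a control.

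**Working it through.** **The plan's own figures.** The documents give no contact count and no adverse-event rate. Their only design calculation is the sample size. It reproduces, and this point does not depend on it: for physical exercise versus control (means 23.90 and 22.08, SDs 3.5 and 4.9, two-sided 5%, 80% power) an unequal-variance t calculation gives 87 per group; 87/0.8 = 108.75, rounded up to 109; 3 x 109 = 327. The 109 is used below only to put illustrative counts on a scale.

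**Scheduled contacts per participant** (Protocol, Interventions and Outcomes)

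- Supervised sessions: 3 per week x 24 weeks = 72 in each exercise arm, 0 in control.
- Lectures: 24/4 = 6 in every arm.
- Post-baseline assessments: 2 in every arm (weeks 24 and 36).

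| Counting rule | Exercise | Control | Difference | Ratio |
|---|---|---|---|---|
| 6 lectures, 2 assessments | 80 | 8 | 72 | 10.0 |
| 7 lectures (weeks 0 and 24 both counted), 2 assessments | 81 | 9 | 72 | 9.0 |
| 7 lectures, baseline assessment also counted | 82 | 10 | 72 | 8.2 |

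The difference is 72 under every rule, and all of it falls in weeks 0-24. After week 24 every arm has one scheduled contact, at week 36. If attendance were 70% to 90% (an assumption), the difference in attended sessions would be 72 x 0.7 = 50 to 72 x 0.9 = 65.

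**What unequal capture would do.** Capture rates are not in the documents; these are assumptions. With equal true rates, the apparent ratio is capture in exercise divided by capture in control:

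- 0.9/0.9 = 1.0
- 0.9/0.7 = 1.29
- 0.9/0.5 = 1.80

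A true ratio of 0.75 would be recorded as 0.75 x 1.29 = 0.96 or 0.75 x 1.80 = 1.35.

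**Illustrative counts.** Expected participants with a recorded event = 109 x true risk x capture, with the same assumed true risk in both arms. The last column is the approximate chance that a two-sided 5% comparison of two proportions shows a significant excess in exercise.

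| True risk | Capture | Exercise | Control | Chance of spurious p < 0.05 |
|---|---|---|---|---|
| 5% | 90% v 70% | 4.9 | 3.8 | 6% |
| 5% | 90% v 50% | 4.9 | 2.7 | 12% |
| 20% | 90% v 70% | 19.6 | 15.3 | 12% |
| 20% | 90% v 50% | 19.6 | 10.9 | 40% |

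If events are rare, the problem is mainly a distorted estimate rather than false significance.

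**The case against.** The strongest reply is that a contact is not an enquiry. No section says that instructors ask about, record or report adverse events; their stated role is to supervise exercise. The Safety section covers every participant throughout the trial, and the Quality Control section refers to uniform training, a common implementation plan, standard operating procedures and monitoring visits. Case report forms also exist. Any of these might contain a standard set of adverse-event questions, and none is reproduced. All arms also share the lectures and assessments, where events could be asked about equally. Adverse events are not a primary or secondary outcome, the SAP's adverse-event text is descriptive, and the likely direction of error is to overstate the harm of exercise.

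Much of this stands. It rules out the stronger reading that a reader might infer: that counts will differ from surveillance alone, with control events largely lost. The documents do not show that sessions are used to detect events or that controls go unasked. A ratio of 78/6 = 13, from sessions and lectures alone, also overstates the contrast because it leaves out the assessments that all arms attend.

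It does not remove the point. General references to procedures do not specify equal ascertainment, and the shared contacts are not assigned this purpose. Nor are the counts purely descriptive: the Protocol's Statistical Analysis section says that all collected data will be compared across the three groups.

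**Conclusion.** The point holds as a risk, not a certainty. Neither document sets an adverse-event enquiry common to all arms, and by schedule each exercise participant has 72 more contacts than a control in weeks 0-24 (80 against 8 over the trial). Recorded falls and hypoglycaemia in exercise versus control can differ for that reason, and the plan gives no means of telling this apart from a true effect.

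The size cannot be derived from the documents. The ratios of 1.29 and 1.80 rest entirely on assumed capture of 90% against 70% or 50%; with equal capture there is no distortion. The contact gap does not touch Tai Chi Chuan versus walking, which have the same schedule throughout, or the MoCA primary endpoint. The long interval from week 24 to week 36 weakens capture in all arms alike and does not itself favour one. This is a worthwhile, inexpensive improvement to the safety comparison.

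**What to change.** **Protocol, Safety.** Ask every participant in all three arms the same short fixed question set (falls, hypoglycaemia, any other event since last asked) at each 4-weekly lecture and at the week 24 and week 36 assessments. Record for each event whether it was found by this enquiry or at an exercise session.

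**SAP 4.1.2.** Present the exercise-versus-control comparison on events from the common enquiry. Alongside it, report all recorded events by arm and by source of detection. Both are needed: a comparison restricted to recalled events could drop a fall witnessed at a session and later forgotten, and no exercise-session event should be missing from the safety report.

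If collection has already finished (the documents' tense is mixed), label events by source where records allow and qualify the comparison accordingly.

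**Cost.** A few minutes at contacts that already exist, with no added visits and no change to sample size. The Protocol mentions only the lecturer at the lectures, so someone must be assigned to ask the questions. The between-arm counts would still rely on recall over up to 4 weeks, and 12 weeks between weeks 24 and 36. Frequent session contact might still prompt better recall in the exercise arms, so the change reduces the imbalance without guaranteeing its removal.

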23	4.4 Interim analysis		
24	4.5 multi-center difference		
25	5 Statistical analysis		
26	5.1 Data management and general analysis		
27	5.2 Analysis of primary endpoint		
28	5.3 Analysis of other endpoints		
29	5.4 Sensitivity analysis		
30	5.5 Software and significant level of the statistical analyses		
31			
32			

33 1 Introduction

The patients with type 2 diabetes mellitus (T2DM) is expected to rise to 439 million in 2030, accounting for 7.7% the population in the world. There are nearly 10 million T2DM patients with mild cognitive impairment (MCI) among people over 65 years old, accounting for about 8% of the people over 65 years old in China. The medical cost for T2DM patients with MCI is 2.5 to 4 times higher than those without T2DM. And T2DM will increase the risk of cognitive impairment, and lead to various complications which will bring serious social and medical economic burden.

40 It is critically important to identify effective treatments to enhance functional status of T2DM patients 41 with MCI. Exercise has been shown to be beneficial for both type 2 diabetes and mild cognitive 42 dysfunction patients. As a Chinese traditional mind-body exercise that consists of both physical and 43 mediation components, Tai Chi Chuan has been proved to be helpful in global cognition, memory, 44 executive function and attention of MCI, and blood sugar of T2DM. However, the evidence of the 45 effect of Tai Chi Chuan on T2DM patients with MCI is limited. The purpose of this study is to explore 46 the effect of Tai Chi Chuan treating T2DM patients with MCI in cognitive function, blood glucose and 47 biochemistry profile.

48 2 Methods

49 2.1 Ethical Approval

50 This study will be conducted by 4 clinical research centers in China. The study was registered 51 with https://clinicaltrials.gov/. (Register Number: NCT04416841), and approved by the Ethics 52 Committee of (1) The Second People's Hospital Affiliated to Fujian University of Traditional Chinese 53 Medicine, Fuzhou, Fujian, China (approval No. 2020KY-004-02), (2) The Second People's Hospital 54 Affiliated to Heilongjiang University of Traditional Chinese Medicine (approval No.2020-K24), (3) 55 Xiyuan Hospital of China Academy of Chinese Medical Sciences, Beijing, China (approval No. 56 2020XLA033-2), and (4) Shenzhen Bao'an District People's Hospital, Shenzhen, China (approval 57 No.BYL20200409). All participants provided written informed consent. Furthermore, a Data Security 58 and Monitoring Committee has been established.

59

60 2.2 Study design

61 This is a multi-center, randomized controlled, parallel-group study. The patients will be randomly 62 divided in 1:1:1 ratio into Tai Chi Chuan group, fitness walking group and control group. This study 63 aims to explore the effect of Tai Chi Chuan treating T2DM patients with MCI in cognitive function, 64 blood glucose and biochemistry profile.

65 2.3 Randomization and Blinding

After signing the informed consent forms, the patients will be enrolled according to the inclusion and
exclusion criteria. The patients who meet the eligibility criteria will be randomized into three groups. A
statistician unrelated to the trial randomly allocated participants after their enrolment using a secure,
central web-based randomization system. The random sequence was generated by SAS version 9.4

- 70 (SAS Institute Inc) with a randomized block size of six and stratified by center. The allocation
- 71 concealment was also conducted by the Research Electronic Data Capture (REDCap).
- 72 3 Study outcome variables
- 73 3.1 Primary outcome variable
- 74 Global cognition-Montreal Cognitive Assessment (MoCA) at 36 weeks
- 75 3.2 Secondary outcome variables
- 76 1) Global cognition-Montreal Cognitive Assessment (MoCA) at 24 weeks
- 2) Memory function-Wechsler memory scale at 24, 36 weeks
- 78 3) Digital Symbol test at 24, 36 weeks
- 79 4) Trial Making Test part B at 24, 36 weeks
- **80** 5) Boston naming test at 24, 36 weeks
- 81 6) Rey-Osterrieth complex graphics test at 24, 36 weeks
- 82 7) Blood glucose metabolism profiles at 24, 36 weeks: fasting blood glucose, glycated hemoglobin
- 83 (HbA1c), homeostasis model assessment of insulin resistance (HOMA-IR), advanced glycation end
- 84 products/soluble receptor of advanced glycation end products (AGE/sRAGE).

85 4 General considerations

86 4.1 Population

87 4.1.1 Sample size

88 To drive all the primary hypothesis tests, the sample size was estimated by using the PASS 15.0 89 software. Based on a previous study¹ and a pilot study we did. sample size required for each individual 90 hypothesis testing was estimated at the two-sided α level 0.05. With other assumptions, the estimated 91 sample sizes were summarized in **table 1**. Comparisons between Tai Chi Chuan and fitness walking 92 were not made due to lack of trial data. To ensure adequate power for each individual hypothesis 93 testing, at least 87 samples were required for each group, which was 109 cases per group considering 94 20% dropout rate. Therefore, the total sample size needed for this study was 327 cases.

- 96
- 97
- 98
- 99

⁹⁵

101 102

103

104

105

Table 1. Sample sizes required for each individual hypothesis testing

Endpoint	Comparison	Assumptions	Sample Size	
primary	Tai Chi Chuan vs.	•Two sided $\alpha = 0.05$	$SS_{TCC} = 37$	
Endpoint	Control	●80% power	$SS_{Control} = 37$	
(MOCA)		●1:1 randomization ratio		
		 Superiority design 		
		•Means _{TCC} = 24.24		
		$Means_{Control} = 22.44$		
		●Standard deviation _{TCC}		
		= 2.677		
		Standard deviation _{Control}		
		= 2.734		
	Physical exercise vs.	•Two sided $\alpha = 0.05$	$SS_{FT} = 87$	
	Control	• 80% power	$SS_{Control} = 87$	
		●1:1 randomization ratio		
		 Superiority design 		
		•Means _{PE} = 23.90		
		$Means_{Control} = 22.08$		
		●Standard deviation _{PE}		
		=3.5		
		Standard deviation _{Control}		
		=4.9		
SS = Sample Size; TCC = Tai Chi Chuan; PE= Physical exercise; FT = Fitness walking				

106

107 4.1.2 Data set

108 Intention-to-treat (ITT) refers to all eligible patients who were randomized to treatment, include
 109 drop-out cases. Multiple imputation methods were used for missing observations.

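### One fixed block size of six within each centre would let site staff who know it and track earlier allocations deduce up to 20% of assignments

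*Combined protocol and SAP*

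**What the plan says.** **Block size.** The protocol (Randomization and concealment) describes a "randomization system for group randomization (group size of 6"), and SAP 2.3 says "with a randomized block size of six and stratified by center". Each gives one number, and neither mentions varying sizes. Stratification by centre appears only in the SAP, which names four centres (SAP 2.1: "This study will be conducted by 4 clinical research centers in China").

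**Allocation ratio.** "Subjects were randomized 1:1:1 into Tai Chi Chuan group, fitness" walking and control (protocol, Randomization and concealment), so a block of six is two places per arm.

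**Who is blinded.** The protocol states that "blinding is not possible for participants in exercise-intervention" research. The roles it names as unaware of group are "the study outcome assessors and statistical analysts will have" no such knowledge. The coordinator who screens candidates is not on that list.

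**Who judges eligibility.** In the protocol's Recruitment section the clinical research coordinator ("CRC) will evaluate their suitability using inclusion and exclusion" criteria) decides suitability before randomization.

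**Safeguards.** SAP 2.3 provides for a statistician unrelated to the trial who allocates after enrolment through a "central web-based randomization system. The random sequence was generated by SAS version 9.4", with concealment through REDCap.

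**Primary analysis.** SAP 4.2 rules out covariate adjustment for the primary endpoint. The adjusted comparison in SAP 5.2 uses self-reported dietary calories and physical activity, not baseline MoCA.

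**The concern.** A central system hides the future list. It does not stop anyone from inferring the next assignment from past ones when three conditions hold: the block size is fixed and known, blocks close within a centre, and past assignments are visible. The plan meets the first and, through the SAP, the second. The third is likely at least in part, because two arms attend supervised exercise three times a week and the control arm does not.

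Some eligibility criteria leave room for judgement, such as whether daily function is intact enough for MCI rather than dementia, or whether a condition makes exercise unsafe. A recruiter who knows the next arm can delay or steer a candidate. The arms would then differ in who enters them, and blinded outcome assessment does not correct that. An unadjusted comparison of MoCA at 36 weeks would carry the difference into the primary result.

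**Working it through.** **The plan's own related figure.** The documents give no figure for predictability, so the only number to reproduce is the sample size. For exercise versus control in SAP Table 1 (means 23.90 and 22.08, SDs 3.5 and 4.9, two-sided 0.05, 80% power), an unequal-variance t test gives 87 per group. Then 87 / 0.80 = 108.75, rounded up to 109, and 3 × 109 = 327. This matches.

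**Assignments known with certainty.** Inputs: three arms, blocks of six, two places per arm (protocol and SAP 2.3). A place is certain when only one arm has places left in the block.

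- Positions 1 to 4: never certain, because at least three places remain and no arm has more than two.
- Position 5: certain if the last two places belong to the same arm, 3 × (2/6) × (1/5) = 1/5.
- Position 6: always certain.

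Share = (1/5 + 1) / 6 = 0.200. Enumerating all 90 orderings gives the same value.

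**Count in this trial.** With complete blocks only, 0.20 × 327 = 65.4. Four centres leave some last blocks incomplete. With even recruitment (82, 82, 82 and 81; an assumption) each centre has 13 complete blocks, so 4 × 13 × 1.2 = 62.4, or 19.1%. Over every possible split of 327 across four centres the expected count runs from 62.4 to 64.8 (19.1% to 19.8%).

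**Partial knowledge, complete blocks, same observer.**

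| Position | At least one arm ruled out | Best guess correct |
|---|---|---|
| 1 | 0 | 1/3 |
| 2 | 0 | 2/5 |
| 3 | 1/5 | 1/2 |
| 4 | 3/5 | 8/15 |
| 5 | 1 | 3/5 |
| 6 | 1 | 1 |
| Mean | 46.7% | 56.1% |

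Chance alone would give 33.3% correct guesses. In a centre of 82 with its last block incomplete, the best-guess rate is (13 × 3.367 + 1.767) / 82 = 55.5%.

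**Mixed block sizes.** Simulated with 82 patients per centre (assumed) and an observer who knows the set of sizes and sees every earlier allocation at the centre:

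| Block sizes | Certain | Best guess correct |
|---|---|---|
| Fixed 6 | 19.0% | about 55.5% |
| Random 6/9 | about 5% | about 54% |
| Random 6/9/12 | 2.4% | 52.4% |

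A larger fixed size helps less: 14.3% certain with 9 and 11.1% with 12, in complete blocks.

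**What it could do to the result (illustration).** By symmetry about 20% of each arm is predictable. Suppose steering on those places alone shifts their mean MoCA by d points, upward in Tai Chi and downward in control. The bias in the contrast is 0.20d + 0.20d = 0.40d. The documents give no value for d:

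- d = 0.5: 0.2 points, or 0.2 / 1.80 = 11% of the planned Tai Chi versus control difference (24.24 − 22.44 = 1.80).
- d = 1: 0.4 points, or 22%.

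**The case against.** A reader might infer that a fifth of assignments were known to site staff, or that selection took place. The documents support neither. The 20% is a ceiling. It needs one person who knows the block size, knows that blocks close within the centre, has followed every earlier allocation there in order, and also screens. The documents establish only that a coordinator screens and that participants are not blinded. The protocol, which prints the block size, does not mention centre stratification. Someone relying on the protocol alone would think the order across all four centres was needed. It is also too strong to call the trial simply open-label, since assessors and analysts are blinded. All of this stands and limits the claim to a vulnerability.

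The safeguards in SAP 2.3 are real: site staff neither hold nor run the list, and allocation follows enrolment. They do not answer the point, because deduction uses past visible assignments and takes place before the candidate is enrolled. Nothing in the documents says that the size was withheld from sites or that the coordinator was kept unaware of earlier allocations.

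Two further objections stand. Mixing sizes does little against a recruiter who acts on a best guess, since success falls by only about three percentage points. The remedy also has value only before enrolment closes. SAP 5.2 already reports that adjusted and unadjusted findings agreed, which suggests that the trial may be over.

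The SAP's phrase about a randomized block size might be read as varying sizes. With one number given, and the protocol agreeing, that reading is not tenable.

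**Conclusion.** The point holds as a weakness in allocation concealment. Under the stated single block size, a fully informed observer at a centre could deduce up to 20% of assignments (62 to 65 of 327) and could rule out at least one arm for 46.7% of places in complete blocks. This assumes knowledge of the block size and the stratification, and complete tracking of allocations at that centre. The documents neither confirm nor exclude those conditions. Fixed blocks with central allocation remain a valid design, and no internal contradiction or invalid test is involved. The possible bias depends on an unknown degree of steering, and the planned unadjusted primary analysis would not correct it.

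**What to change.** **If enrolment is open.** Generate each centre's list with randomly mixed block sizes, for example 6, 9 and 12. Keep the sizes out of the protocol and all site documents until enrolment closes. If recruitment is already under way, apply this to the unissued part of each centre's list from the next block boundary.

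The cost is a few lines in the randomization program and a sentence each in the protocol and SAP. The downside is a larger possible imbalance within a centre at any moment: up to 4 between two arms, inside a block of 12, instead of 2. The main gain is the removal of certainty, with only a small reduction in guessing.

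**If enrolment has closed.** The prospective change no longer applies. State who at each centre knew the block size and the earlier allocations, and whether the screening coordinator was among them. Compare baseline characteristics, including MoCA, between predictable and unpredictable block positions, by arm. This needs only the allocation list and baseline data. With about 21 predictable places per arm (62.4 / 3 = 20.8 to 64.8 / 3 = 21.6), it can reveal a gross pattern, but finding none would not exclude modest selection.
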